1.2 Schedule of Assessments (SoA)

Table 2. Schedule of Assessments (SoA)

Study day relative to 1 st vaccination	-28 to -1	1	2	4	8	15	29											
Study day relative to 2 nd vaccination							1	2	4	8	15	29	57	180	ET ¹	U ²		
Visit window in days			+1	+1	+1	+/- 1	+3	+1	+1	+1	+/- 1	+/- 4	+/- 4	+/- 7				
Study visit	00 ³	01	01a	02	02a	03	04	04a	05	05a	06	07	08	09				
Visit type ⁴	I	I	P	I	P	I	I	P	I	P	I	I	I	I	I	I		
Obtain informed consent ⁵	X																	
Assessment of eligibility ⁶	X	X					X											
Review of medical history	X	X					X											
Concomitant meds	X ⁷	X	X	X	X	X	X	X	X	X	X	X	X	X	X ⁸	X ⁸		
Vital signs ⁹	X	X		X		X	X		X		X	X	X ¹⁰	X ¹⁰	X ^{8,10}	X ¹⁰		
Perform physical exam ¹¹	X																	
Height and weight ¹²	X																	
Counseling ¹³	X	X		X		X	X		X		X				X ⁸			
Review of contraceptive/menstrual history ¹⁴	X	X					X											
Pregnancy test ^{15, 16}	X	X					X											
HIV antibody ELISA, anti-HCV antibody, HBsAg	X																	
Blood for clinical screening labs ¹⁷	X																	
Urine for screening lab ¹⁸	X																	
Targeted physical exam ¹⁹		X ¹⁹		X ¹⁹		X ¹⁹	X ¹⁹		X ¹⁹		X ¹⁹	X ¹⁹	X ¹⁹	X ¹⁹	X ¹⁹	X ¹⁹		
Randomization ²⁰		X																
Vaccination ²¹		X					X											

Study day relative to 1 st vaccination	-28 to -1	1	2	4	8	15	29								ET ¹	U ²		
Study day relative to 2 nd vaccination							1	2	4	8	15	29	57	180				
Visit window in days			+1	+1	+1	+/- 1	+3	+1	+1	+1	+/- 1	+/- 4	+/- 4	+/- 7				
Study visit	00 ³	01	01a	02	02a	03	04	04a	05	05a	06	07	08	09				
Visit type ⁴	I	I	P	I	P	I	I	P	I	P	I	I	I	I	I	I		
Evaluate vaccination site				X		X			X		X				X ⁸	X ⁸		
Blood for clinical safety labs ¹⁶ ¹⁷		X		X		X	X		X		X				X ²²	X ²²		
Urine for safety lab ²³		X				X	X				X				X ²²	X ²²		
Blood for YFV neutralizing assays ¹⁶		X				X	X				X	X	X	X ²⁶	X ²²	X ²²		
Blood for viremia testing				X					X						X ²²	X ²²		
Identification of unsolicited adverse events ²⁴		X	X	X	X	X	X	X	X	X	X	X			X ⁸	X ⁸		
Identification of medically-attended adverse events ²⁴		X	X	X	X	X	X	X	X	X	X	X	X	X	X	X		
Identification of serious adverse events ²⁴		X	X	X	X	X	X	X	X	X	X	X	X	X	X	X		
Identification of new onset of chronic condition ²⁴		X	X	X	X	X	X	X	X	X	X	X	X	X	X	X		
Review memory aid data			X	X	X			X	X	X					X ²⁵	X ²⁵		

¹ET=early termination visit.

²U=unscheduled visit.

³Screening procedures are performed at visit 00.

⁴Visit type: I=In-person, P= Phone.

⁵Consent process must be completed and informed consent form signed before any study-related procedures are conducted.

⁶Review inclusion/exclusion criteria.

⁷Obtain concomitant medications (prescription and over-the-counter drugs taken within the previous 60 days).

Study day relative to 1 st vaccination	-28 to -1	1	2	4	8	15	29									
Study day relative to 2 nd vaccination							1	2	4	8	15	29	57	180	ET ¹	U ²
Visit window in days			+1	+1	+1	+/- 1	+3	+1	+1	+1	+/- 1	+/- 4	+/- 4	+/- 7		
Study visit	00 ³	01	01a	02	02a	03	04	04a	05	05a	06	07	08	09		
Visit type ⁴	I	I	P	I	P	I	I	P	I	P	I	I	I	I	I	I

⁸Perform assessment if before Visit 07.

⁹Vital signs including oral temperature, blood pressure and pulse.

¹⁰Required at this visit if clinically indicated.

¹¹Physical exam assessing general appearance and the following areas/systems: skin, lymph nodes, HEENT, neck, respiratory, cardiovascular, pulmonary, abdomen, extremities, musculoskeletal, and neurological.

¹²Obtain weight and height, calculate BMI.

¹³Counseling for avoidance of pregnancy and, at screening only, for HIV testing.

¹⁴For women of childbearing potential.

¹⁵Pregnancy test must be negative and be completed at screening (serum test) and within 24 hours prior to vaccination (urine test) for women of childbearing potential.

¹⁶On vaccination visits, these items should be completed prior to vaccination.

¹⁷White blood cell count, hemoglobin, platelets, sodium, potassium, bicarbonate, calcium, creatinine, glucose (non-fasting), ALT, AST, and total bilirubin.

¹⁸For glucose and protein by dipstick.

¹⁹Targeted physical exam if indicated by medical history.

²⁰Subjects will be randomized to receive HydroVax-002 YFV (varying dosages) at day 1 and day 29 or to receive saline placebo at day 1 and day 29.

²¹All subjects will be observed for a minimum of 30 minutes following vaccination.

²²Perform procedure if indicated.

²³For glucose, protein, blood, and leukocyte esterase. If positive for blood or leukocyte esterase perform microscopic urine exam.

²⁴Collection of AE, MAAE, SAE and NOCMC begin after first vaccination.

²⁵Perform assessment if before Visit 06.

²⁶Serum sample collected for exploratory serological analysis.

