3. STUDY OBJECTIVES AND OUTCOME MEASURES

The overall objective of the study is to evaluate the safety and immunogenicity of two different dose levels of HydroVax-002 YFV.

OBJECTIVES	ENDPOINTS (Outcome Measures)
Primary	

To assess the safety, reactogenicity, and tolerability of the HydroVax-002 YFV vaccine administered intramuscularly in a two-dose series on Days 1 and 29 at a dose of 1 mcg or a dose of 5 mcg
	
 • Occurrence of all serious adverse events (SAEs) at any time during the study • Occurrence of all Grade 3 unsolicited adverse events (AEs) from first vaccination through Day 29 after the second vaccination • Occurrence of all Grade 3 laboratory toxicities from first vaccination through Day 15 after the second vaccination • Occurrence of solicited local AE and reactogenicity signs and symptoms in the 7 days after each vaccination • Occurrence of solicited systemic AE and reactogenicity signs and symptoms in the 7 days after each vaccination • Occurrence of any AE through Day 29 after the second vaccination
Secondary	

To assess YFV-specific neutralizing antibody responses after a first dose and after a second dose of HydroVax-002 YFV vaccine given at dose levels of 1 mcg and 5 mcg
	
 • Percentage of subjects achieving seroconversion ($\geq 1:10$ in plaque reduction neutralizing titer [PRNT₅₀] titer) at Day 29 after first vaccination and at Day 29 after second vaccination • Geometric mean neutralizing titers at Days 15 and 29 after first vaccination and at Days 15, 29, and 57 following second vaccination • Reverse cumulative distribution curve of neutralizing titers on Days 15 and 29 after first vaccination and at Days 15, 29, and 57 after the second vaccination for each dose group and for all dose groups combined
Exploratory	

To assess long-term YFV-specific neutralizing antibody responses after a second dose of HydroVax-002 YFV vaccine given at dose levels of 1 mcg and 5 mcg
	
• Geometric mean neutralizing titers at Day 180 following second vaccination• Reverse cumulative distribution curve of neutralizing titers on Day 180 after the second vaccination for each dose group and for all dose groups combined
---	--

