7.1.2 Individual Halting Criteria

Individual Halting Criteria must be reviewed by the site PI prior to administration of the second study vaccination for each subject. It is the responsibility of the site to ensure that any subject meeting the below criteria are discontinued from receiving study product; however, the Emmes BMM or safety monitor may be consulted as needed.

The second study vaccination will not be administered to a subject if any of the following criteria are met, as determined by the site PI:

- Serious adverse event associated with study vaccination.
- Pregnancy in a female subject.
- Type 1 hypersensitivity associated with study product.
- Grade 3 systemic reaction associated with study product.
- Grade 3 local reaction (with the exception of erythema/induration) associated with study product (e.g., pain).
- Grade 2 or higher fever within the first 24 hours following the initial vaccination.
- Medical condition for which continued participation, in the opinion of the site principal investigator or appropriate sub-investigator, would pose a risk to the subject or would be likely to confound interpretation of the results.
- Presence of signs or symptoms that could confound or confuse assessment of study vaccine reactogenicity. For subjects with injection site or systemic signs or symptoms, or with an acute illness, including but not limited to an oral temperature greater than or equal to 100.4°F, the second study vaccination should be postponed/deferred until signs, symptoms, or acute illness have resolved and still within the acceptable protocol-specified window for that visit. If outside this window, the Blinded Medical Monitor must first approve the second study vaccination and the documentation of approval should be filed in the subject's chart.
- Any unresolved or continuing solicited or unsolicited Grade 3 adverse event after first vaccination. An unresolved or continuing Grade 1 or Grade 2 adverse event is permissible unless, in the opinion of the site principal investigator or appropriate subinvestigator, it would render study vaccination unsafe or interfere with the evaluation of responses.
- Grade 2 or higher clinical safety laboratory result that does not decrease to Grade 1 or below prior to the second study vaccination. For a subject to receive the second study vaccination, the most recently evaluated clinical safety laboratory values obtained prior to the second study vaccination must be Grade 1 or less. The

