8.2.2 Safety Clinical Laboratory Tests

Safety labs will be conducted on blood samples obtained on Days 4 and 15 after each vaccination and on the day of, but prior to, administration of the first and second vaccination (day 29 after first vaccination). Safety labs include hematology tests (hemoglobin, WBC, and platelet count) and blood chemistry tests (sodium, potassium, bicarbonate, calcium, creatinine, glucose [non-fasting], ALT, AST, and total bilirubin).

Urine will be tested by dipstick to evaluate glucose, protein, blood, and leukocyte esterase on days 1, 15 and 29 after first vaccination and day 15 after second vaccination.

Safety labs will be tested locally by Duke University Health System Clinical Laboratories.

For laboratory values outside the site's reference ranges, the site PI will document clinical significance in the eCRF. Any result that is deemed clinically significant but does not meet the protocol's grading criteria ([Appendix A](#)) should either be repeated by the study site, or the subject referred for appropriate clinical follow-up.

For any result that meets the protocol's grading criteria (whether or not it is deemed clinically significant), the PI will also assess relationship to study product, action taken with product, and whether the subject was discontinued due to the event. Graded laboratory abnormalities should be followed until either a return to normal or are judged to be stable, as determined by the PI.

In the absence of a diagnosis, any clinical safety laboratory test result that meets the definition of an SAE as determined by the investigator (e.g., life-threatening) must be reported as an SAE using the AE/SAE form set.

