9.4.2 Analysis of Primary Outcome Measures (Safety)

Solicited AEs and laboratory toxicities will be analyzed by taking the most severe response over the follow-up period, dichotomizing into a binary variable (none or mild versus moderate or severe) and using exact confidence intervals to summarize the reactogenicity and toxicity rates. Tabular and graphical summaries of events will be presented for each solicited symptom, by type (local/systemic/toxicity), severity (none or mild, moderate or severe), and time point post-vaccination.

Unsolicited AEs will be coded by the Medical Dictionary for Regulatory Activities (MedDRA) for preferred term and system organ class. The rate and exact 95% confidence intervals of AEs in aggregate, and by MedDRA categories, will be computed. SAEs will be reported by a detailed listing showing the type, MedDRA coding, relevant dates (vaccination and adverse event), severity, relatedness, and outcome for each event. Primary outcome measures include:

- Occurrence of all serious adverse events (SAEs) at any time during the study.
- Occurrence of all Grade 3 unsolicited adverse events (AEs) from first vaccination through day 29 after the second vaccination.
- Occurrence of all Grade 3 laboratory toxicities from first vaccination through day 15 after the second vaccination.
- Occurrence of solicited local AE and reactogenicity signs and symptoms in the 7 days after each vaccination.
- Occurrence of solicited systemic AE and reactogenicity signs and symptoms in the 7 days after each vaccination.
- Occurrence of any AE through day 29 after the second vaccination.

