	Max Severity Post Baseline	HydroVax-002 YFV -1 mcg	XX	X	X.X	X	X.X	X	X.X	X	X.X
		HydroVax-002 YFV -5 mcg	XX	X	X.X	X	X.X	X	X.X	X	X.X
		Placebo	XX	X	X.X	X	X.X	X	X.X	X	X.X

Repeat for all laboratory parameters...

The "Max Post Baseline" rows indicate the maximum severity experienced by each subject at any time point post baseline, including unscheduled assessments.

N = Number of subjects in the Safety population with available laboratory results.

Implementation note: This table will be repeated for all hematology, blood chemistry and urinalysis parameters.

Table 29: Abnormal Laboratory Results Related to Study Treatment by Parameter, Maximum Severity, Study Day, Treatment Group and Parameter – Any Parameter

Parameter	Time Point	Treatment Group	Mild/ Grade 1			Moderate/ Grade 2		Severe/ Grade 3	
			N	n	%	n	%	n	%
[Parameter 1]	Day 4 Post-Dose 1	HydroVax-002 YFV -1 mcg	XX	x	x.x	x	x.x	x	x.x
		HydroVax-002 YFV -5 mcg	XX	x	x.x	x	x.x	x	x.x
		Placebo	XX	x	x.x	x	x.x	x	x.x
	Day 15 Post-Dose 1	HydroVax-002 YFV -1 mcg	XX	x	x.x	x	x.x	x	x.x
		HydroVax-002 YFV -5 mcg	XX	x	x.x	x	x.x	x	x.x
		Placebo	XX	x	x.x	x	x.x	x	x.x
	Day 29 Post-Dose 1	HydroVax-002 YFV -1 mcg	XX	x	x.x	x	x.x	x	x.x
		HydroVax-002 YFV -5 mcg	XX	x	x.x	x	x.x	x	x.x
		Placebo	XX	x	x.x	x	x.x	x	x.x
	Day 4 Post-Dose 2	HydroVax-002 YFV -1 mcg	XX	x	x.x	x	x.x	x	x.x
		HydroVax-002 YFV -5 mcg	XX	x	x.x	x	x.x	x	x.x
		Placebo	XX	x	x.x	x	x.x	x	x.x
	Day 15 Post-Dose 2	HydroVax-002 YFV -1 mcg	XX	x	x.x	x	x.x	x	x.x
		HydroVax-002 YFV -5 mcg	XX	x	x.x	x	x.x	x	x.x
		Placebo	XX	x	x.x	x	x.x	x	x.x
	Max Severity Post Baseline	HydroVax-002 YFV -1 mcg	XX	x	x.x	x	x.x	x	x.x
		HydroVax-002 YFV -5 mcg	XX	x	x.x	x	x.x	x	x.x
		Placebo	XX	x	x.x	x	x.x	x	x.x

Repeat for all laboratory parameters...

The “Max Post Baseline” rows indicate the maximum severity experienced by each subject at any time point post baseline, including unscheduled assessments.

N = Number of subjects in the Safety population with available laboratory results.

Implementation note: This table will be repeated for all hematology, blood chemistry and urinalysis parameters.

Table 30: PRNT₅₀ Geometric Mean Titer (GMT) and Log Neutralizing Titer Index (LNI) Results with 95% Confidence Intervals by Study Day and Treatment Group, Full Analysis Population

Visit	HydroVax-002 YFV 1 mcg			HydroVax-002 YFV 5 mcg			Placebo		
	N	GMT	95% CI	N	GMT	95% CI	N	GMT	95% CI
PRNT₅₀									
Day 1 (pre-vaccination)	XX	X.XX	X.XX, X.XX	XX	X.XX	X.XX, X.XX	XX	X.XX	X.XX, X.XX

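### Dipstick blood is graded by colour alone with no record of menses, so a menstrual urine sample can count as a Grade 3 laboratory toxicity in a primary safety endpoint

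*Protocol*

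**What the plan says.** Protocol section 8.2.2 schedules the safety dipstick (glucose, protein, blood, leukocyte esterase) "on days 1, 15 and 29 after first vaccination and day 15 after second vaccination". These are Visits 01, 03, 04 and 06 of Table 2. Footnote 23 to that table adds "If positive for blood or leukocyte esterase perform microscopic urine exam".

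Appendix A, Table 14 grades dipstick blood 1+ as Grade 1, 2+ as Grade 2 and above 2+ as Grade 3. Its footnotes exempt trace protein at screening and class blood as a safety test that is not done at screening. Under section 8.2.2, a result that meets the grading criteria is handled as graded whatever its clinical significance.

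The primary endpoint is "Occurrence of all Grade 3 laboratory toxicities from first vaccination through Day 15 after the second vaccination" (section 3, repeated in 9.4.2), with no filter for relatedness. Section 9.4.2 also takes each subject's most severe laboratory toxicity over follow-up and splits it into none or mild against moderate or severe. SAP section 8.4 includes urinalysis among the laboratory tests to be summarized. SAP Table 28 is repeated for each urinalysis parameter and reports the "maximum severity experienced by each subject at any time point post baseline, including unscheduled assessments".

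The Table 2 row "Review of contraceptive/menstrual history" is marked at Visits 00, 01 and 04 only. Section 8.3 allows one repeat measurement at the investigator's judgment. Section 7.1.2 lists, among the reasons to withhold dose 2, a "Grade 2 or higher clinical safety laboratory result that does not decrease to Grade 1 or below prior to the second study vaccination".

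**The concern.** The trial enrolls women aged 18 to under 50 and collects urine on fixed days, so some samples will fall during menses. Nothing in the protocol or SAP tells the site to note this, and nothing tells the analyst what to do with such a reading. Menstrual history is not reviewed at Visits 03 and 06, when the two Day 15 samples are taken. Where it is reviewed, it stands beside contraception and is not tied to the urine result.

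The provisions that might catch a menstrual reading do not change the count. Microscopy is ordered but feeds no grade, table or endpoint. A clean repeat leaves the first value in place, because the worst value stands. A normal physiological finding can therefore be reported as a Grade 3 laboratory toxicity in a trial whose stated purpose (section 9.1) is to estimate event rates. The error can only raise the absolute rate, and with 10 vaccinees per dose a single event is visible. The same laboratory data go to the Safety Monitoring Committee before escalation.

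**Working it through.** **The plan's own figures.** With n = 10 and a true rate of 15%, the chance of at least one event is 1 − 0.85^10 = 80.3%, as in protocol Table 8; the other eight rows also reproduce. The exact two-sided upper bound for 0/10 is 1 − 0.025^(1/10) = 0.3085, against the 30.8% in section 9.2.1. Neither figure is in dispute.

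**Path from the reading to the endpoint.**
1. Blood above 2+ is Grade 3 (Table 14).
2. It is graded regardless of clinical significance (section 8.2.2).
3. All Grade 3 laboratory toxicities count, whatever the relatedness (sections 3 and 9.4.2).
4. The most severe value is used, unscheduled values included (section 9.4.2; SAP Table 28).
5. A 2+ reading follows the same path into the moderate-or-severe rate.

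**Size, as an illustration.** From the documents: post-dose urine falls on study Days 15, 29 and 43 (Day 15 after a Day 29 second dose), with 10 vaccinees per dose. Assumed, because the documents give no figures:
- regular 28-day cycle
- bleeding days m = 5 (range 3 to 7)
- cycling women per 10 vaccinees w = 5 (range 3 to 7)
- chance that a menstrual sample reads above 2+, q = 0.5 (range 0.25 to 0.75)

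The chance of menses on a given day is f = m/28 = 5/28 = 17.9%. Days 15 and 43 are 28 days apart and share a cycle phase; Day 29 is in another. So a woman is menstruating at one or more post-dose samples with probability 2f = 35.7%.

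The chance that she has at least one reading above 2+ is f[1 − (1 − q)²] + fq = 0.1786 × 0.75 + 0.1786 × 0.5 = 0.223. Per dose group:
- expected subjects with a false Grade 3: 5 × 0.223 = 1.1
- chance of at least one: 1 − (1 − 0.223)^5 = 72%

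| Case | m | w | q | Per woman | Expected | At least one |
|---|---|---|---|---|---|---|
| Low | 3 | 3 | 0.25 | 0.074 | 0.2 | 20% |
| Central | 5 | 5 | 0.50 | 0.223 | 1.1 | 72% |
| High | 7 | 7 | 0.75 | 0.422 | 3.0 | 98% |

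Changing q alone to 0.25 or 0.75 gives 48% or 83%. If the three visits were independent in phase, the central per-woman chance would be 1 − (1 − 0.0893)^3 = 0.245, and the group figure 1 − (1 − 0.245)^5 = 75%. The phase assumption matters little.

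**Effect on the estimate.** One false event turns 0/10 (upper bound 30.8%) into 1/10, with exact 95% CI 0.3 to 44.5%.

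**The case against.** Several points on the other side have force.

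- **The event would be visible.** Table 28 gives urine blood its own rows with placebo alongside, Table 9 splits Grade 3 laboratory toxicities by relatedness, and Listing 12 has an alternative-etiology column. Placebo women are equally exposed. This stands, but visibility does not take the event out of the endpoint. Without a menses record at Visits 03 and 06, the etiology may not be documented. Five placebo subjects say little about background.
- **Counting all blood is a cautious choice** for a first-in-human vaccine against a virus whose disease includes hemorrhage and renal failure. This is fair, and it is a reason to keep such readings listed. The plan does not say that it makes this choice, and it orders microscopy without using it.
- **Day 1 supplies a baseline.** Under a 28-day cycle it shares a phase with Day 29, so part of the effect can be recognised. Leaving Day 29 out, the central per-woman chance is 0.1786 × 0.75 = 0.134, and the group figure 1 − (1 − 0.134)^5 = 51%. But the plan does not subtract baseline.
- **The inputs are external.** This stands in full: the documents do not state that a menstrual sample can read 2+ or more, and the 20 to 98% range shows how much turns on the assumptions.
- **The manual of procedures and data collection forms may deal with menses.** They are not available here, so the gap is shown for the protocol and SAP only.

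A reader might go further and infer that menses at Visit 04 costs a subject dose 2 and her place in the per-protocol set. The documents do not establish that. The Table 2 urine row lacks footnote 16, which requires completion before vaccination, and no text says when the urine result is known. The section 7.1.2 criterion looks to the most recent value, the visit has a +3 day window, and the Blinded Medical Monitor may approve dosing beyond it. Per-protocol exclusion needs a missed dose or one substantially out of window. Nor would menses by itself trigger the study halting rule, which requires events considered related.

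**Conclusion.** The gap is real for the primary safety count. Followed as written, the plan scores a menstrual dipstick reading above 2+ as a Grade 3 laboratory toxicity, scores 2+ as moderate or severe, and keeps that score after a clean repeat. On the stated assumptions the chance of at least one false Grade 3 in a dose group is about 72% (range 20 to 98%), and one event changes 0/10 to 1/10. The direction follows from the documents; the size is illustrative.

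An effect on dose 2 is possible but uncertain, and a delay is as possible as a missed dose. The point warrants a cheap improvement to data capture and counting. It does not put the design in question.

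**What to change.** 1. Add a yes/no 'menses today' item to the CRF at each urine safety visit (01, 03, 04, 06).
2. In SAP section 8.4 and the notes to Tables 9, 28 and 29, state that dipstick blood collected during menses is listed and shown separately. It is not counted in the Grade 3 laboratory endpoint or the moderate-or-severe rate unless a repeat taken after menses confirms it.
3. State how the reflex microscopy result is used.
4. Limit the rule to blood. The documents give no basis for treating leukocyte esterase the same way.

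Placing the rule in the SAP leaves the Table 14 grades, and so dosing eligibility, untouched. Separately, the sponsor should reconcile Table 14, Table 2 footnotes 16 and 23, and section 7.1.2 for such readings; which rule should apply is the sponsor's decision.

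The cost is one CRF question at four existing visits and a few sentences in the SAP. The downside is that true hematuria on a menses day is listed but not counted unless the repeat confirms it.
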